2.4. Use of Teplizumab in Children

The majority of new cases of T1D occur in children under the age of 18. Moreover, given that the duration of diabetes is a significant risk factor for the development of diabetic complications and the clearly recognized difficulty in attaining excellent metabolic control of diabetes during adolescence. Diagnosis of T1D before the age of 20 incurs greater morbidity and loss of life years than when the diagnosis is made in adulthood. In the TN-10 trial, 72% of the participants were

children. The adverse event experience was not significantly different in adults and children. Altogether, more than 470 children have received teplizumab in clinical trials.

The study procedures, while greater than minimal risk, offers the possibility of benefit due to the close monitoring for all participants and the delay in diagnosis of T1D. Assent of children along with consent of their guardians will be obtained, as appropriate, prior to any study procedures.

Please refer to the Teplizumab IB for further non-clinical and clinical information on the antibody.

2.5. Benefit/Risk Assessment

Type 1 diabetes (T1D) is an autoimmune disease that results in a severe metabolic disease of glucose dysregulation. T1D is associated with significant short- and long-term complications and early death. Even with the best metabolic control using the most current insulins and glycemic monitoring devices, these risks are not eliminated. There is an urgent need to develop a disease modifying therapy for T1D.

Clinical studies with teplizumab in T1D have shown that it is effective in preserving beta cell function (as measured by C-peptide) and hence endogenous insulin production ([Herold 2019](#)). In the previous Protégé Study, teplizumab resulted in a statistically significant preservation of C-peptide, compared to placebo, at 2 years. As described in natural history studies, preservation of residual beta cell function (as measured by C-peptide levels) is protective against short-(hypoglycemic episodes) and long-term complications of T1D, including retinopathy, nephropathy and other cardiovascular events ([Steffes 2003](#), [Sorensen 2013](#), [Lachin 2014](#), [Kuhtreuber 2015](#)).

The main risks of teplizumab consist of transient lymphopenia and transient self-limited (mild to moderate) rash. Cytokine release syndrome is infrequent (~6%) and there is no overall increased risk of clinical infection or cancers.

Given the potential for important benefit in short- and long-term T1D outcomes compared to the transient, mild to moderate risks of teplizumab, the prospect of benefit outweighs the risk of participating in this study.

More detailed information about the known and expected benefits and risks and reasonably expected adverse events of teplizumab may be found in the IB.

3. Objectives and Endpoints

Objectives	Endpoints
Primary	

 To evaluate the safety and tolerability of teplizumab treatment, administered intravenously (IV) to participants in the TN-10 trial who have developed T1D. 	
 Incidence of treatment-emergent adverse events (TEAEs), adverse events of special interest (AESIs), and serious adverse events (SAEs)
Secondary	

 To evaluate the pharmacokinetics (PK) and immunogenicity of teplizumab To evaluate whether teplizumab treatment reduces the loss of β cells, over 78 weeks (18 months), in individuals with recent diagnosis of T1D. To evaluate key clinical parameters of diabetes management, including insulin use, hemoglobin A1c (HbA1c), and clinically important hypoglycemic episodes over 78 weeks To evaluate whether treatment with teplizumab increases the frequency of exhausted T cells 	
 Levels of teplizumab in the serum and anti-drug antibodies The area under the time-versus-concentration curve (AUC) of C-peptide after a 4-hour (4h) mixed meal tolerance test (MMTT), a measure of endogenous insulin production and β cell function, over 78 weeks HbA1c levels; insulin use, defined as a daily average in units per kilogram per day (U/kg/day); and frequency of clinically important hypoglycemic episodes over 78 weeks Frequency of CD8+ TIGIT+ KLRG1+ T cells

4. Study Design

4.1. Overall Design

The is a single-arm, multicenter, open-label clinical trial.

Teplizumab-treated and placebo participants in the TN-10 trial who develop clinical type 1 diabetes after the conclusion of that trial, are eligible to enroll and receive teplizumab treatment in this open-label study within one year of clinical T1D diagnosis.

Number of Participants:

Up to 30 participants may be enrolled in this study.

Treatment and Study Duration:

All participants will receive a 12-day course of teplizumab given through daily IV infusion. Participants will have a screening period of up to 4 weeks, a treatment period of 12 days, and a follow-up period of up to 78 weeks (18 months) from the first dose of treatment.

4.2. Scientific Rationale for Study Design

It is recognized that participants eligible for this study have undergone further decline in beta cell mass and function since their participation in the TN-10 trial, leading to the need for exogenous insulin replacement in order to maintain glycemic control. At this juncture, it is critical to preserve the remaining beta cell function as this leads to better short-term (ie, hypoglycemic episodes) and long-term outcomes including retinopathy, nephropathy and other cardiovascular events ([Steffes 2003](#), [Sorensen 2013](#), [Lachin 2014](#), [Kuhtreuber 2015](#)). Phase 2 and Phase 3 clinical trials with teplizumab have consistently shown significant preservation of beta cell function as measured by C-peptide in patients with newly diagnosed T1D ([Hagopian 2013](#); [Herold 2013a](#); [Herold 2013b](#); [Herold 2019](#)). Therefore, it is anticipated that the benefit of teplizumab treatment on preservation of beta cell function may be realized in previous participants of the TN-10 study who now have developed clinical type 1 diabetes.

Between 20% and 56% of teplizumab treated patients develop anti-drug antibodies that may be neutralizing antibodies (NAb). These antibodies can be detected within 2 weeks after the drug has been given. They may affect the immunologic effects of additional courses of teplizumab treatment, but a safety concern has not been identified – second courses of teplizumab did not have an increased frequency of adverse events compared to the first course. In this study, the responses to teplizumab treatment in participants with and without anti-drug antibodies will be analyzed. The time interval between the first (under the TN-10 protocol) and second course of teplizumab treatment in this study (PRV-031-002) is longer than has previously been tested and therefore, the effect of anti-drug antibodies is not known. Thus, these study participants are different from those who previously have received two courses of teplizumab. As eligible and consenting placebo participants in the TN-10 trial will also be treated with teplizumab upon the diagnosis of clinical T1D, the immunologic effects of teplizumab in the placebo group, who will receive teplizumab for the first time, will serve as a comparator to individuals previously treated with teplizumab.

4.3. Justification for Dose

In previous clinical studies of teplizumab in T1D, a number of dosing regimens have been evaluated that have included children and/or adults. These studies have evaluated single multi-day courses of teplizumab and 2 multi-day courses either 6 or 12 months apart. Although the goals, stage of T1D, and entry criteria differed between these studies, all have shown that teplizumab was well tolerated with an acceptable safety profile, and an ability to preserve β cell function and improve clinical outcomes in study populations or specific sub-populations. It is these effects that support further evaluation and clinical development of teplizumab as a first-in-class therapy for children and adolescents newly diagnosed with T1D ([Herold 2002](#), [Sherry 2011](#), [Hagopian 2013](#), [Herold 2005](#), [Herold 2013a](#), [Herold 2013b](#)).

Of note, the 14-day regimen evaluated in Protégé (and other previous studies including the TN-10) The most extensive and detailed evaluation of teplizumab in T1D is from the Phase 2/3 “Protégé” study in which 2 multi-day courses of teplizumab were given 6 months apart in children and adults 8 to 35 years old who were diagnosed with T1D within 12 weeks of T1D diagnosis. In that study, three dosing regimens of teplizumab were evaluated and included: (1) a 14-day course with a cumulative dose of 9.0 mg/ m^2 ; (2) a 14-day course with a cumulative dose of 3.0 mg/ m^2 ; and (3) a 6-day course with a cumulative dose of 2.4 mg/ m^2 . In the open-label Phase 2 segment of Protégé, participants received the 14-day regimen of 9.0 mg/ m^2 /course at enrollment and 26 weeks later to assess safety and tolerability before the double-blind study was started. The Phase 3 segment studied the three teplizumab dosing regimens in comparison to placebo. The open label Phase 2 segment of Protégé enrolled 38 participants, and the randomized, double-blind Phase 3 segment enrolled 207, 102, and 106 teplizumab-treated participants, respectively, and the placebo arm 98 participants ([Sherry 2011](#), [Hagopian 2013](#)).

In addition to assessments of safety and efficacy, the Protégé study conducted extensive PK and immunogenicity evaluations. From this data, a detailed population PK model has been developed using a two-compartment (peripheral and central) model with saturable binding kinetics incorporating body surface area (BSA), proportional dosing, and teplizumab AUC, trough concentration, and peak concentration. These findings showed that PK was independent of age, gender, race, region, disease state or onset, although it was influenced by antidrug-antibody response.

As described earlier, although the previously untested and unevaluated composite primary endpoint was not met in the entire study population of Protégé, a positive effect of teplizumab in T1D was confirmed in Protégé subpopulations, supporting findings from a number of previous clinical studies. Specifically, participants from certain regions (eg, the United States) who were 8-17 years old, who had teplizumab initiated within 6 weeks of T1D diagnosis and with higher C-peptide levels at study entry showed significant retention of endogenous insulin production through 2 years compared to placebo treated participants.

A 14-day course necessitates participants and their parents or guardians (required by pediatric participants) to be available every day for 2 entire consecutive weeks and associated weekends. This requirement is seen to be particularly challenging to children and adolescents and their families due to work and school obligations and therefore may have a negative influence on recruitment and retention as well as a significant bias in a pivotal study.

[figure not shown]
With the realization of the potential negative impact on many aspects of the clinical trial of a 14-day treatment course combined with the significant experience with teplizumab, in this study we propose to use a regimen that is more acceptable to participants and their families that delivers clinically overlapping exposures that could support approval for teplizumab.

We propose to modify the dosing regimen to 12 days: Day 1: 106 $\mu\text{g}/\text{m}^2$, Day 2: 425 $\mu\text{g}/\text{m}^2$, and Days 3-12: 850 $\mu\text{g}/\text{m}^2/\text{day}$. During the first 2 days of ramp-up, approximately 5.9% of the total dose is given. In the last 10 days, ~94% of the total dose is delivered in equally divided doses.

Compared to a 14-day dosing regimen, this study's 12-day teplizumab course has a modified 2-day ramp-up phase but also has a 10-day fixed-, maximal dosing period like the 14-day course. Based on calculations, the amount of teplizumab given in the 12- and 14-day approach only differs by 0.005 mg/m^2 . But due to practical aspects of rounding and calculating the BSA and a given dose, these courses are considered clinically equivalent.

As shown in the PK simulations in Figure 4, the first 2 doses in the 14-day regimen are calculated to have very low, almost negligible, serum concentrations with serum concentrations of the last 11 doses of both regimens that are superimposable. In both instances, >90% of the total dose per course is given in the final 10 days in similar equally divided doses (0.850 mg/m^2 in the 12-day course versus 0.826 mg/m^2 in the 14-day course). The first 2 days of the 14-day course delivers a nominal amount (ie <2.0%) of the course's total dose. The final trough concentrations (426±220 ng/mL [14-day regimen] and 435±225 ng/mL [12-day regimen]), as well as the elimination times are overlapping in both regimens.

Figure 4: PK Simulation of 12-Day and 14-Day Dosing Regimens

Taken together, this study will evaluate a more participant and family-friendly approach to deliver the same dose of 9.0 mg/m^2 of teplizumab over a course of 12 days, which has been shown to be

well tolerated, safe and effective in preserving β cell function. Because of the similarities and overlap of the regimens and exposures, data from this study can be combined with data from other studies to support the application and approval for teplizumab as a disease modifying therapy for the study population in those recently diagnosed with T1D.

4.4. End of Study Definition

A participant is considered to have completed the study if he/she has completed all phases of the study including the last visit shown in the Schedule of Events (Section 1.3).

The end of the study is defined as the date of the last visit of the last participant in the study.

5. Study Population

5.1. Inclusion Criteria

Participants are eligible to be included in the study only if all of the following criteria are met:

1. Previous participant in the TN-10 study.
2. Participant has received a diagnosis of T1D after the conclusion of the TN-10 study, according to the criteria from the American Diabetes Association (ADA).
3. Participant is able to initiate teplizumab treatment required in this study within 1 year of T1D diagnosis.
4. If participant is female with reproductive potential, she must have a negative pregnancy test prior to enrollment and be willing to avoid pregnancy for at least 18 months from the first dose of study drug.
5. Participant is willing and medically able to postpone live vaccine immunizations for 1 year after receiving the last dose of study drug in this study.
6. Participant is willing to forego other forms of experimental treatment during the entire study.
7. Participant and/or guardian has given informed consent and assent as applicable.

5.2. Exclusion Criteria

Participants will be excluded from the study if any of the following criteria is met at screening or before the first dose is given:

1. Lymphopenia (< 1000 lymphocytes/ μ L)
2. Neutropenia (< 1500 polymorphonuclear cells [PMNs]/ μ L)
3. Thrombocytopenia (< 150,000 platelets/ μ L)
4. Anemia (hemoglobin < 10 g/dL)
5. Aspartate aminotransferase (AST) or alanine aminotransferase (ALT) >1.5 x upper limit of normal (ULN)
6. Total bilirubin >1.5 x ULN. Exception: participants with the diagnosis of Gilbert's syndrome may be eligible if they have no other causes leading to hyperbilirubinemia.
7. Chronic active infection except localized skin infections. This may be discussed with the Medical Monitor on a case by case basis.
8. Participant has any of the following regarding tuberculosis (TB):
 - A history of latent or active TB
 - Signs and/or symptoms of TB
 - Recent close contact with a person with known or suspected active TB, unless appropriate isoniazid prophylaxis for tuberculosis was given
 - A history of a chest X-ray consistent with active TB or old, inactive TB,
 - A history of a positive purified protein derivative (PPD) skin test result (>10 mm induration)
 - At screening is positive or repeatedly indeterminate with an approved interferon-gamma release assay (IGRA; eg, QuantiFERON-TB test) or PPD.

- If required by local, regional or national regulations, a recent (within 3 months) chest X-ray or one conducted at screening read by a qualified radiologist consistent with current, active TB or old, inactive TB
9. Vaccination with a live virus within 8 weeks before first dose of the study drug
 10. Vaccination with a killed virus within 4 weeks before first dose of the study drug
 11. A history of infectious mononucleosis within the 3 months before screening.
 12. Laboratory or clinical evidence of acute infection with EBV or CMV.
 13. Serological evidence of current or past human immunodeficiency virus (HIV), hepatitis B virus (HBV) or hepatitis C virus (HCV) infection.
 14. Currently pregnant or lactating or planned pregnancy within 18 months 2 years after receiving the last dose of the study drug
 15. Chronic use of steroids or other immunosuppressive agents.
 16. A history of asthma or atopic disease requiring chronic corticosteroid treatment.
 17. Untreated hypothyroidism or active Graves' disease.
 18. Current use of non-insulin pharmaceuticals or dietary supplements that may affect glycemic control.
 19. Participation in any therapeutic drug or vaccine clinical trial within 12 weeks before the first dose of study drug.
 20. Any condition that, in the opinion of the investigator, would interfere with the study conduct or the safety of the participant.

5.3. Enrollment

Potential study participants will be identified through previous participation in the TN-10 trial. TN-10 participants, regardless of whether they received teplizumab or placebo in that study, are invited and screened for this study if they have been diagnosed with T1D and can receive teplizumab within 12 months of the diagnosis.

6. Study Drug Dosing

6.1. Study Drug Administered

All participants will receive an IV infusion of teplizumab once daily for 12 consecutive days.

The participant's body surface area (BSA) will be calculated by the study pharmacist using the Mosteller formula. The BSA will be calculated on Study Day 1 and will be based on the participant's height and weight on that day. This calculation will be used for the doses given over the entire 12-day treatment course. For dosing purposes, the participant's BSA should be rounded up to the nearest tenth place regardless of the number in the hundredth position. For example, if the BSA is 1.61 m², it will be rounded up to 1.7 m²; if the BSA is 1.67 m², it will also be rounded up to 1.7 m². The dose should be rounded to the nearest whole number.

The drug dosing is:

Day 1: 106 µg/m²

Day 2: 425 µg/m²

Days 3-12: 850 µg/m² daily

Total per course: 9.0 mg/m²

The Mosteller formula is as follows:

$$\text{BSA (m}^2\text{)} = ([\text{Height(cm)} \times \text{Weight(kg)}]/ 3600)^{1/2}$$

Teplizumab is administered via an IV infusion over a minimum of 30 minutes in the research or hospital setting. The daily time of the infusion should be consistent but may be adjusted by a time window of ± 4 hours on each day. If there are signs or symptoms of infusion reaction during the 60-minute observation period, the participant should be observed for an addition al 60 minutes or until the reaction resolves, whichever is longer.

6.2. Preparation/Handling/Storage/Accountability

The formulation of teplizumab consists of 10 mM sodium phosphate, 150 mM sodium chloride, and 0.05 mg/mL Tween 80, with pH 6.1.

Final drug product will be provided at a concentration of 1 mg/mL for a total of 2 mg of recoverable drug product per vial.

The vials should be stored upright at 2°–8°C and must not be frozen or shaken. Because there is no preservative and drug loss occur over time, administration of the study drug should begin as soon as possible and no later than 2 hours after preparation. The drug may be prepared into a bag for infusion and delivered by gravity or by infusion pump. Intravenous drug delivery devices, including IV bags and tubing, must be composed of polyvinyl chloride (PVC). Refer to Pharmacy manual for details.

Laboratory studies that will be obtained prior to each dose are described in the Schedule of Events (Section 1.3) and Appendix 2 (Section 10.2). The same-day results of chemistries (including liver function tests [LFTs]), WBC counts, hemoglobin, hematocrits and platelets must be reviewed prior to commencement of the drug infusion on each dosing day.

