1.3. Schedule of Events

Week	-4	1							2				4	12	26	52	78	ET		
Month	-1	1												3	6	12	18	ET		
Day	Screen ¹	1	2	3	4	5	6	7	8	9	10	11	12	28	84	182	364	546	ET	
Visit window		Not applicable												± 4 days	± 4 days	± 2 wks	± 2 wks			
Visit number	-1	1	2	3	4	5	6	7	8	9	10	11	12	13	14	15	16	17	ET	
Informed consent/assent	X																			
Inclusion/exclusion criteria review	X	X																		
Medical history	X	X	X	X	X			X						X		X	X	X	X	
Height (cm) & weight (kg)	X	X															X	X	X	
Vital signs ²	X	X	X	X	X	X	X	X	X	X	X	X	X	X	X	X	X	X	X	
Physical exam (C=Complete; P=Partial)	C	P													P	P	P	P	C	
Previous/concomitant medications	X	X	X	X	X	X	X	X	X	X	X	X	X	X	X	X	X	X	X	
Adverse event review	X	X	X	X	X	X	X	X	X	X	X	X	X	X	X	X	X	X	X	
Teplizumab dose calculation		X																		
Premedication		X	X	X	X	X	X ³													
Teplizumab administration ⁴		X	X	X	X	X	X	X	X	X	X	X	X							
Tuberculosis testing (PPD or IGRA)	X																			
Chemistry and LFTs ^{5,6}	X	X	X						X					X	X	X	X	X	X	
CBC with differential and platelets ⁵	X	X	X	X	X		X		X					X	X		X	X	X	
Teplizumab levels ⁷		X			X					X				X	X		X	X	X	
Anti-teplizumab antibodies ⁷		X			X					X				X	X		X	X	X	
EBV/CMV serology ⁸	X																			
EBV and CMV viral loads ⁸	X														X	X				
HIV, HBV, HCV serology ⁸	X																			
4h MMT ⁹		X															X	X	X	X
T1D autoantibodies	X																			
Urine pregnancy test (WOCBP only)	X	X					X							X		X	X	X	X	
Urine ketones ¹⁰																				
HbA1c	X															X	X	X	X	
Mechanistic assessments ¹¹	X	X												X		X	X	X	X	

Abbreviations: ALT=alanine aminotransferase, AST=aspartate aminotransferase, BP=blood pressure, BUN=blood urea nitrogen, CBC=complete blood count, CMV=cytomegalovirus, EBV=Epstein-Barr virus, EBNA=Epstein-Barr nuclear antigen, ET=early termination visit, HbA1c=hemoglobin A1c, HBV=hepatitis B virus,

HCV=hepatitis C virus, HIV=human immunodeficiency virus, Ig=immunoglobulin IGRA= interferon-gamma release assay, LDH=lactate dehydrogenase, MMTT= mixed-meal tolerance test, PPD=purified protein derivative, T1D=type 1 diabetes, WOCBP=women of childbearing potential

Footnotes:

1. Enrollment must occur within 4 weeks of screening.
2. Vital signs include temperature, pulse, blood pressure, and respiration. On dosing days, vital signs should be collected pre-dose, 15 minutes after the start of infusion, at the end of infusion, and 60 minutes after the end of infusion.

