3. Pre-treatment medications are required on Days 1-5, optional on Days 6-12.
4. Teplizumab dose: Day 1: 106 $\mu\text{g}/\text{m}^2$, Day 2: 425 $\mu\text{g}/\text{m}^2$, Days 3 to 12: 850 $\mu\text{g}/\text{m}^2$ daily.
5. These results must be reviewed prior to drug administration (see Section 8.1.2). CBC with differentials are done locally.
6. Liver function tests (ALT, AST, LDH, alkaline phosphatase, total protein, albumin, total and direct bilirubin) and chemistries (sodium, potassium, chloride, CO₂, glucose, BUN, creatine) are done locally. Day 1 samples should be obtained pre-dose.
7. Blood samples for the measurements of teplizumab trough levels and anti-drug antibodies are to be obtained within 30 minutes before study drug infusion.
8. Serology assessments include EBV IgG and IgM, EBNA, CMV IgG and IgM, HIV, HBV, and HCV are done locally. All participants, regardless of whether they are seropositive or seronegative for EBV and CMV at screening, will be tested for viral load by the central lab at the indicated visits.
9. MMTT: 4-hour samples should be collected pre-dose on Day 1. Samples will be archived for possible future pro-insulin analysis.
10. In participants who have discontinued insulin therapy, urine ketones should be checked once daily.
11. Includes samples for RNA, plasma, serum, DNA, and measurements of B and T cell numbers and function to understand the effect of therapy on the immune system and infectious disease. Day 1 samples should be obtained pre-dose.

2. Introduction

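### Protocol 6.2 requires same-day chemistry/LFT and blood-count results before all 12 infusions, but the Schedule of Events it cites has both on only 3 of 12 dosing days as the table reads

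*Protocol*

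**What the plan says.** Protocol 6.1 sets the number of infusions: "All participants will receive an IV infusion of teplizumab once daily for 12 consecutive days".

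Protocol 6.2 makes two statements about laboratory tests. The first says where sampling is defined: "Laboratory studies that will be obtained prior to each dose are described in the Schedule of Events", with Appendix 2 (10.2) as the second source. The next sentence lists chemistry including LFTs, white cell count, hemoglobin, hematocrit and platelets, and says that the same-day results "must be reviewed prior to commencement of the drug infusion on each dosing day".

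The Schedule of Events (1.3) carries these tests in two rows, "Chemistry and LFTs" and "CBC with differential and platelets". Neither row is marked on every dosing day. Footnote 5, attached to both, asks for review before drug is given and cross-refers to 8.1.2, which describes only the Visit 1 baseline review.

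Appendix 2 lists the local tests and refers back to 1.3 for timing. Section 7.1 says that samples are those listed in 1.3, yet has the investigator review results before dosing on every treatment day.

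**The concern.** A same-day result requires a sample that day. If the Schedule has no draw on a dosing day, the sentence in 6.2 cannot be met without an unscheduled one. A site that works from the Schedule then departs from a mandatory instruction on most dosing days. A site that works from 6.2 draws blood that the Schedule does not list.

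Two things depend on the answer.

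- **Dosing decisions.** Section 7.1 has hold limits for ALT/AST, bilirubin, platelets and hemoglobin. Section 7.2 has stop limits for the same measures plus neutrophils. A limit can first be crossed on record only on a day when a sample is taken. Both sections provide for repeat tests after an abnormal value. What is unclear is whether a first test is required on the other dosing days.
- **Safety data.** Safety is the primary objective, and several adverse events of special interest are defined by laboratory values (Protocol 10.3.3; SAP 7.7.1). These include liver tests, platelets, neutrophils on two consecutive evaluations and, in the SAP, a lymphocyte count that stays low for at least 7 days. If sites sample at different frequencies, ascertainment differs between them. The protocol-deviation listing in SAP 7.3 also has no settled rule for a missing pre-dose result.

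**Working it through.** **Inputs.** Twelve dosing days (6.1). Required by 6.2: chemistry/LFTs and blood counts, same day, on each of them. Scheduled by 1.3: the marks in the two laboratory rows, matched to the Day header.

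**Count of the Schedule as it reads.**

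| | Dosing days marked | Scheduled | Not scheduled |
|---|---|---|---|
| Required by 6.2 | 1–12 | 12 of 12 | 0 |
| Chemistry/LFTs | 1, 2, 8 | 3 of 12 | 12 − 3 = 9 (Days 3–7, 9–12) |
| Blood count (CBC) | 1, 2, 3, 4, 6, 8 | 6 of 12 | 12 − 6 = 6 (Days 5, 7, 9–12) |
| Both | 1, 2, 8 | 3 of 12 | 9 |
| Neither | 5, 7, 9–12 | – | 6 of 12 |

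The runs of infusions with no scheduled LFT are Days 3–7 (five) and Days 9–12 (four). The only consecutive dosing days with scheduled LFTs are Days 1 and 2.

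**Alignment.** The table comes from PDF text and some late columns appear to have moved. The header, dosing, vital-signs, chemistry and CBC rows have the same number of fields, and the dosing row falls exactly on Days 1–12. However, the mixed-meal test (MMTT) row runs one field past the header. The teplizumab-level row also lacks Days 12 and 182, which SAP 7.8.6 lists.

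- If the marks after Day 8 in the two laboratory rows belong one column to the left, Day 12 gains both tests. LFTs are then on 4 of 12 days, CBC on 7, the full set on 4 (Days 1, 2, 8, 12) and neither on 5 (Days 5, 7, 9–11).
- Moving all, only the early, or only the late marks one column in either direction gives LFTs on 2 to 4 of 12 days and CBC on 5 to 7.

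**A bound that needs no alignment.** The chemistry row has 10 marks in all: screening, three dosing days, five follow-up visits and early termination. Even if every one of them fell on a dosing day, 12 − 10 = 2 dosing days would have no LFT. The CBC row has 12 marks, one of them at screening, so at most 11 could fall on dosing days.

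**Blank cells do not mean daily.** Assessments done every day are marked every day. The row "Teplizumab administration" has 12 marks, one per dosing day. Vital signs have 19 marks that include all 12 dosing days, and their footnote says so: "On dosing days, vital signs should be collected pre-dose, 15 minutes after the start of infusion". Concomitant medications and adverse event review are marked in the same way.

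**No other passage supplies the missing draws.** Appendix 2 and footnote 5 add no chemistry or CBC days, and 8.1.2 stops at Visit 1. Section 7.1 contains both versions in one sentence and cannot decide between them.

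**The case against.** The strongest reply is that 6.2 delegates sampling to the Schedule in its first sentence, and that the second sentence is only a review rule: whatever was scheduled that day must be same-day and reviewed before infusion. Footnote 5 and the reference to 1.3 in Section 7.1 fit that reading, and on it a site following the Schedule breaches nothing. The wording of 6.2 does not support it well. The sentence names the tests, requires same-day results and applies to each dosing day, with no limit to scheduled tests. That two sites could reasonably read it differently is itself a reason to amend it.

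The second reply is that 3 of 12 is fragile because of the column drift. This stands for the exact figure, which could be 4 of 12. It does not remove the conflict, because 10 marks cannot cover 12 days.

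The third reply is that the consequence is limited. Repeat tests are provided for, the investigator may hold or stop dosing on judgment under 7.1 and 7.2, and SAP 7.7.2 only lists laboratory results, so no analysis changes. All of that is true. It does not tell a site whether a first test is due on a given dosing day.

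**Conclusion.** The contradiction is real. Section 6.2 requires results on 12 of 12 dosing days, and the Schedule it cites provides the full set on 3 of 12 as it reads. Chemistry/LFTs are absent on 9 days, CBC on 6 and both on 6. These counts assume that the extracted columns are aligned. One-column shifts give LFTs on 2 to 4 days and CBC on 5 to 7. Under any alignment, at least 2 dosing days have no scheduled LFT. The conclusion also rests on reading the mandatory sentence in 6.2 as it is worded. It must be fixed, because a required pre-dose safety check and the table that implements it cannot both be followed. No view is taken here on which schedule is clinically right.

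**What to change.** Reconcile four places so that they name the same tests on the same dosing days:

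- Section 6.2;
- the two laboratory rows of the Schedule (1.3), with footnote 5 and its cross-reference to 8.1.2;
- the opening sentence of Section 7.1;
- Appendix 2. Its Gilbert's syndrome sentence, a related but separate mismatch, calls for an MMTT before each infusion, while the Schedule marks that test on Day 1 only among the dosing days.

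The sponsor's clinical team decides which version stands.

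The cost is a text amendment to one table, one footnote and three sections. No visits are added, because participants already attend on all 12 days. If the Schedule version is kept, no draws are added and only the wording changes. If the 6.2 version is kept, the Schedule gains 9 chemistry/LFT and 6 CBC draws per participant on the counts as read. Allowing for the alignment range, that is 12 − 4 = 8 to 12 − 2 = 10 chemistry draws and 12 − 7 = 5 to 12 − 5 = 7 CBC draws. The added blood volume would have to stay within the limits recognized in Section 8.
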